**10.5 Interim Analysis and Early Stopping Guidelines**

Since the study is open labeled no interim analysis will be performed to inform early stopping guidelines.

## **10.6 Planned Methods of Analysis**

Summary tabulations will be provided for disposition, demographic, baseline, efficacy, and safety data as noted in the following sections.

All eCRF data, lab data, and any outcomes derived from the data will be provided in the patient data listings. Patient data listings will be presented for all patients enrolled into the study. Descriptive summary statistics including n, mean, median, standard deviation, standard error, interquartile range (25th percentile, 75th percentile), and range (minimum, maximum) for continuous variables, and counts and percentages for categorical variables will be used to summarize most data.

### ***10.6.1 Demographic and Baseline Characteristics***

Demographic and Baseline characteristics will be summarized using descriptive statistics by treatment group. All patients enrolled will be included in a summary of patient disposition.

### ***10.6.2 Safety Analysis***

Treatment duration and amount of Study Drug received will be summarized by treatment group and overall.

Injection Site Reactions (ISRs) will be summarized by treatment group, MedDRA preferred term and severity.

#### ***10.6.2.1 Adverse Events***

Treatment duration and amount of Study Drug received will be summarized. Patient incidence rates of all AEs will be tabulated by MedDRA system organ class, and by MedDRA preferred term. Narratives of treatment-emergent deaths, serious and significant AEs, including early withdrawals due to AEs, will also be provided.

All treatment-emergent AEs, all treatment-emergent AEs potentially related to Study Drug, all treatment-emergent serious AEs, and all treatment-emergent serious AEs potentially related to Study Drug will be summarized.

#### ***10.6.2.2 Clinical Laboratory Data***

Laboratory tests to ensure patient safety including chemistry panel, complete blood count (CBC) with differential, coagulation panel, complement, etc., will be summarized by study visit. These safety variables will also be presented as change and percent change from baseline over time after Study Drug administration, as appropriate. In addition, the number of patients who experience abnormalities in clinical laboratory evaluations will be listed.

#### ***10.6.2.3 Vital Signs and Examinations***

Vital signs, weight, and ECG measures will be tabulated by treatment group.

### ***10.6.3 Efficacy Analysis***

Percent change and change from baseline to Month 3 in fasting TG will be summarized. Response rate of patients with fasting serum TG < 750 mg/dL or achieving fasting TG  $\geq$  40% reduction from baseline at Month 3 will be summarized. Response analysis will also be conducted using a range of fasting serum TG thresholds for determination of responder status.

Percent change and change from baseline to Month 3 will also be summarized by treatment group for other fasting lipid measures including ANGPTL3, non-HDL-C, apoB, HDL-C, apoA-1, VLDL-C, and LDL-C, total cholesterol, and fasting total apoC-III.

#### **10.6.4 Pharmacokinetic Analysis**

The plasma PK of AKCEA-ANGPTL3-LRX (as total full length oligonucleotides, including, fully conjugated, partially conjugated, and unconjugated AKCEA-ANGPTL3-LRX) will be assessed following multiple-dose SC administration. The plasma trough levels of AKCEA-ANGPTL3-LRX during treatment period and those during post-treatment follow up period will be descriptively summarized with stratification by subject immunogenicity status if applicable.

#### **10.6.5 Pharmacodynamic Analysis**

The following parameters will be measured throughout the trial: Fasting TGs, plasma angiopoietin-like 3 (ANGPTL3), ANGPTL4, ANGPTL8, total cholesterol (TC), low density lipoprotein cholesterol (LDL-C), high density lipoprotein cholesterol (HDL-C), non-high density lipoprotein cholesterol (non-HDL-C), very low density lipoprotein cholesterol (VLDL-C), total apoC-III, apolipoprotein B-100 (apoB-100), apolipoprotein B-48 (apoB-48), apolipoprotein A-1 (apoA-1), apolipoprotein A-2 (apoA-2), apolipoprotein E (apoE), very-low-density lipoprotein-triglyceride (VLDL-TG), chylomicron-cholesterol (CM-C), chylomicron triglyceride (CM-TG), free fatty acids (FFA), and free glycerol levels.

#### **10.6.6 Immunogenicity Analysis**

Immunogenicity (IM) results (screen positive/negative, confirmed positive/negative or not evaluable, and when applicable, titer of anti-AKCEA-ANGPTL3-LRX antibodies) before, during, and after treatment with AKCEA-ANGPTL3-LRX will be listed. Subject ADA status (positive/negative or not evaluable) for all evaluable patients, along with the study day associated with the first positive IM status emerged (Tfirst, i.e., onset of ADA development), the last positive IM status observed (Tlast), the last ADA sample collection day, and subject - peak titer if applicable, will be listed and study day.

Additionally, the sample and subject IM incidence (number) and incidence rate (percent) will be summarized as the total number and percent of evaluated subjects with antibody negative, positive, and unknown status by treatment group. Furthermore, onset and titer of the ADA response, if applicable, will be summarized as median, quartiles (25% and 75%), and range.

#### **10.6.7 Additional Analyses**

Additional analyses may be performed not specified in this open label study protocol from the data available.

### **11. INVESTIGATOR'S REGULATORY OBLIGATIONS**

#### **11.1 Informed Consent**

The written informed consent document should be prepared in the language(s) of the potential patient population, based on an English version provided by the Sponsor or designee.

Before a subject's participation in the trial, the Investigator is responsible for obtaining written informed consent from the subject or legally acceptable representative after adequate explanation of the aims, methods, anticipated benefits, and potential hazards of the study and before any protocol-specific screening procedures or any Study Drug AKCEA-ANGPTL3-LRX are administered. The subject or

legally acceptable representative must be given sufficient time to consider whether to participate in the study.

The acquisition of informed consent and the subject's agreement or refusal to notify his/her primary care physician should be documented in the subject's medical records and the informed consent form should be signed and personally dated by the subject or a legally acceptable representative and by the person who conducted the informed consent discussion (not necessarily an Investigator). The original signed informed consent form should be retained in the Study Master File and in any other locations required by institutional policy, and a copy of the signed consent form should be provided to the subject or legally acceptable representative.

If a potential subject is illiterate or visually impaired and does not have a legally acceptable representative, the Investigator must provide an impartial witness to read the informed consent form to the subject and must allow for questions. Thereafter, both the subject or legally acceptable representative and the witness must sign the informed consent form to attest that informed consent was freely given and understood.

The sponsor shall maintain all records referred to in the applicable Regulations for a period of 25 years.

### **11.2 Ethical Conduct of the Study**

The Guidelines of the World Medical Association (WMA) Declaration of Helsinki dated October 2002, the applicable regulations and guidelines of current Good Clinical Practice (GCP), as well as the demands of national drug and data protection laws and other applicable regulatory requirements will be strictly followed. The more recent Declaration of Helsinki version from 2013 is not being followed.

### **11.3 Independent Ethics Committee/Institutional Review Board**

A copy of the protocol, proposed informed consent form, other written subject information, and any proposed advertising material must be submitted to the IEC/IRB for written approval. A copy of the written approval of the protocol and informed consent form must be received by the Sponsor or designee before recruitment of subjects into the study and shipment of Study Drug. A copy of the written approval of any other items/materials that must be approved by the Study Center or IEC/IRB must also be received by the Sponsor or designee before recruitment of subjects into the study and shipment of Study Drug. The Investigator's Brochure must be submitted to the IEC/IRB for acknowledgement.

The Investigator must submit to and, where necessary, obtain approval from the IEC/IRB, for all subsequent protocol amendments and changes to the informed consent document. The Investigator should notify the IEC/IRB of deviations from the protocol in accordance with ICH GCP Section 4.5.2. The Investigator should also notify the IEC/IRB of SAEs occurring at the Study Center and other AE reports received from the Sponsor or designee, in accordance with local procedures.

The Investigator will be responsible for obtaining annual IEC/IRB approval/renewal throughout the duration of the study. Copies of the Investigator's reports, all IEC/IRB submissions and the IEC/IRB continuance of approval must be sent to the Sponsor or designee.

### **11.4 Subject Confidentiality**

The Investigator must ensure that the subject's confidentiality is maintained. On the case report forms or other documents submitted to the Sponsor or designee, subjects should be identified by initials (if permitted by local law) and a subject identification number only. Documents that are not for submission

to the Sponsor or designee (e.g., signed informed consent forms) should be kept in strict confidence by the Investigator.

In compliance with Federal and local regulations/ICH GCP Guidelines, it is required that the Investigator and institution permit authorized representatives of the company, of the regulatory agency(s), and the IEC/IRB direct access to review the subject's original medical records for verification of study-related procedures and data. Direct access includes examining, analyzing, verifying, and reproducing any records and reports that are important to the evaluation of the study. The Investigator is obligated to inform and obtain the consent of the subject to permit named representatives to have access to his/her study-related records without violating the confidentiality of the subject.

## **12. ADMINISTRATIVE AND LEGAL OBLIGATIONS**

### **12.1 Protocol Amendments**

Protocol amendments must be made only with the prior approval of the Sponsor or designee. Agreement from the Investigator must be obtained for all protocol amendments and amendments to the informed consent document. The regulatory authority and IEC/IRB must be informed of all amendments and give approval for any amendments likely to affect the safety of the subjects or the conduct of the trial. The Investigator **must** send a copy of the approval letter from the IEC/IRB to the Sponsor or designee.

### **12.2 Study Termination**

The Sponsor or designee reserves the right to terminate the study. The Investigator reserves the right to terminate their participation in the study, according to the terms of the site contract. The Investigator/Sponsor or designee should notify the IEC/IRB in writing of the trial's completion or early termination and send a copy of the notification to the Sponsor or designee.

### **12.3 Study Documentation and Storage**

An electronic case report form (eCRF) utilizing an Electronic Data Capture (EDC) application will be used for this study.

The Investigator should ensure that all appropriately qualified persons to whom he/she has delegated trial duties are recorded on a Sponsor-approved Delegation of Site Responsibilities Form.

Source documents are original documents, data, and records from which the subject's case report form data are obtained. These include but are not limited to hospital records, clinical and office charts, laboratory and pharmacy records, diaries, imaging, and correspondence. Case report form entries may be considered source data if the case report form is the site of the original recording (i.e., there is no other written or electronic record of data).

The Investigator and Study Center staff are responsible for maintaining a comprehensive and centralized filing system of all study-related (essential) documentation in accordance with Section 8 of the ICH Guidelines (E6), suitable for inspection at any time by representatives from the Sponsor or designee and/or applicable regulatory authorities. Elements should include:

- Subject files containing completed case report forms, informed consents, and supporting copies of source documentation

- Study files containing the protocol with all amendments, Investigator's Brochure, copies of pre-study documentation and all correspondence to and from the IEC/IRB and the Sponsor or designee
- If drug supplies are maintained at the Study Center, proof of receipt, Study Drug Product Accountability Record, Return of Study Drug Product for Destruction, final Study Drug product reconciliation, and all drug-related correspondence

In addition, all original source documents supporting entries in the case report forms must be maintained and be readily available.

No study document should be destroyed without prior written agreement between the Sponsor or designee and the Investigator. Should the Investigator wish to assign the study records to another party or move them to another location, he/she must notify the Sponsor or designee.

#### **12.4 Study Monitoring**

The Sponsor representative and regulatory authority inspectors are responsible for contacting and visiting the Investigator for the purpose of inspecting the facilities and, upon request, inspecting the various records of the trial (e.g., case report forms and other pertinent data) provided that subject confidentiality is respected.

The Sponsor monitor or designee is responsible for inspecting the case report forms at regular intervals throughout the study to verify adherence to the protocol; completeness, accuracy, and consistency of the data; and adherence to local regulations on the conduct of clinical research. The monitor should have access to subject medical records and other study-related records needed to verify the entries on the case report forms.

The Investigator agrees to cooperate with the monitor to ensure that any problems detected in the course of these monitoring visits, including delays in completing case report forms, are resolved.

In accordance with ICH GCP and the Sponsor's audit plans, this study may be selected for audit by representatives from the Sponsor's Clinical Quality Assurance Department (or designees). Inspection of Study Center facilities (e.g., pharmacy, drug storage areas, laboratories) and review of study-related records will occur to evaluate the trial conduct and compliance with the protocol, ICH GCP, and applicable regulatory requirements.

To ensure the quality of clinical data a clinical data management review will be performed on subject data received by the Sponsor or designee. During this review, subject data will be checked for consistency, omissions, and any apparent discrepancies. In addition, the data will be reviewed for adherence to the protocol and GCP. To resolve any questions arising from the clinical data management review process, data queries and/or Study Center notifications will be sent to the Study Center for completion and return to Sponsor or designee.

The Principal Investigator will sign and date the indicated places on the case report form. These signatures will indicate that the Principal Investigator inspected or reviewed the data on the case report form, the data queries, and the Study Center notifications, and agrees with the content.

#### **12.5 Language**

Case report forms must be completed in English. Whenever possible, the trade name rather than the generic name for concomitant medications should be recorded and if possible, in English. Generic names

are acceptable if the trade name is unknown. Combination medications should be recorded using their trade name in English if possible.

All written information and other material to be used by subjects and investigative staff must use vocabulary and language that are clearly understood.

#### **12.6 Compensation for Injury**

The Sponsor maintains appropriate insurance coverage for clinical trials and will follow applicable local compensation laws. Subjects will be treated and/or compensated for any study-related illness/injury in accordance with the information provided in the Compensation for Injury section of the Informed Consent document.

## **14. APPENDICES**

## **Appendix A      Schedule of Procedures**

## Appendix A Schedule of Procedures

Study Period	Screen/ Run-in a	Treatment Period										Post-treatment Follow-up		
		-8 to -1	1	3	5	7	9	11	13	14/ET			18	22
Study Week	-56 To -1	1 b	15	29	43	57	71	85	92	94	95	120	148	176
Visit and Testing Window +/- Days	0	0	2	2	2	2	2	2	2	0	0	3	3	3
Informed Consent	X													
Inclusion/Exclusion Criteria	X	X												
Medical History	X													
Height & Weight c	X	X		X		X			X					X
Vital Signs	X	X		X		X			X			X	X	X
Physical Examination d	X	X		X		X			X					X
12- lead ECG (triplicate)	X	X		X		X			X					X
24-hour urine creatinine clearance and protein	X													
Abdominal Pain Assessment	X	X		X		X			X					X
Urinalysis	X	X		X		X			X			X	X	X
Blood Draw e	Chemistry Panel (+ CPK) f,g	X	X	X	X	X	X	X	X			X		X
	CBC with Differential f,g	X	X	X	X	X	X	X	X			X h	X	X
	Serum Lipid Panel	X	X		X		X		X	X		X	X	X
	PD Panel		X		X		X		X	X		X	X	X
	Coagulation (aPTT, PT, INR)	X	X		X		X			X		X	X	X
	Complement Markers C5A, Bb	X	X							X				
	hsCRP	X	X		X		X			X				X
	Hepatitis B, C, HIV, TSH, Free T 4	X												
	Plasma PK i		X 		X 	X 	X 	X 		X		X	X	X
	Genetic Testing j	X												
	Anti-ANGPTL3-L RX Antibodies		X 		X 		X 			X		X		X
	FSH (women only, if applicable) k	X												
	Serum Pregnancy Test k	X	X		X		X		X	X		X	X	X

Appendix A Schedule of Procedures *Continued*

Study Period	Screen/ Run-in a	Treatment Period										Post-treatment Follow-up												
		1	3	5	7	9	11	13	14/ET			18	22	26										
Study Week	-8 to -1	1 b	15	29	43	57	71	85	92	94	95	120	148	176										
Study Day	-56 To -1	1 b	15	29	43	57	71	85	92	94	95	120	148	176										
Visit and Testing Window +/- Days	0	0	2	2	2	2	2	2	2	0	0	3	3	3										
HbA1C and delipidated free glycerol	X																							
Archived Serum & Plasma m		X								X				X										
Post-Prandial Assessment	X i									X i	X i	X i												
Platelet aggregation		X		X		X				X				X										
Study Drug Administration		WEEKLY SUBCUTANEOUS ADMINISTRATION OF STUDY DRUG (Week 1 through Week 13)																						
Adverse Events	TO BE COLLECTED FROM TIME OF INFORMED CONSENT TO END OF FOLLOW-UP PERIOD																							
Concomitant Medication	TO BE COLLECTED FROM TIME OF INFORMED CONSENT TO END OF FOLLOW-UP PERIOD																							

All procedures and study samples are to be performed pre-dose at respective visits, unless specified

- a Subject starts the tightly controlled diet, if needed.
- b After 6 weeks on the controlled diet, patients will have baseline measurements and be assessed for qualification of enrollment.
- c Height is only required on Day 1.
- d Full physical exam to be given at Screening and abbreviated physical exam to be given during treatment and follow-up period as indicated to assess changes from screening.
- e Blood samples to be collected after an overnight fast of at least 10 hours and preferably not more than 12 hours, unless tests are repeated for safety reasons.
- f If the platelet value, serum creatinine or liver enzyme tests are uninterpretable (e.g., due to clumping, hemolysis or quantity not sufficient) a repeat blood specimen should be re-drawn as soon as possible (ideally within 7 days). All platelet count results will be reviewed promptly (within 48 hours of receipt) by the Investigator. Any case of a platelet count  $\leq 50,000/\text{mm}^3$  should be reported in an expedited fashion to the Sponsor.
- g If not done as part of a Study Center visit, assessments and procedures to be conducted by either a home healthcare service or the Study Center. Subject Study Center visits must be no more than 4 weeks apart during the treatment period.
- h During follow-up period, hematology sampling for platelet values are taken every 14 days for 6 weeks after last dose of Study Drug, then at Week 22 and Week 26 Follow-up visits.
- i Refer to [Appendix C](#) for PK Sampling schedule.
- j Genetic testing will only be performed for eligibility if no documented genetic testing in medical history.
- k Women who are not surgically sterile or post-menopausal.

**Appendix A Schedule of Procedures *Continued***

- I The postprandial assessment for Screening will only be performed after other eligibility criteria are met. Subjects will be provided a standardized meal during Screening visit with instructions on when and how to consume and will return to the study center on Day -1 (2 days after consumption) for pre-dose postprandial assessments. Subjects will again be provided standardized meal at the Week 14 visit (Day 92) and will return to the site 2 days later (Day 94) plus one more day (Day 95) for post-dose postprandial assessments.
- m Serum and plasma samples will be collected and stored for follow-up exploration of laboratory findings and/or AEs (e.g., measurement of cytokine and/or chemokine levels, measurement of additional markers of kidney function, measurement of antibodies, etc.) and will be retained until completion of the final study report.

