#### ***6.1.1 Screening***

Written informed consent for the study will be obtained prior to the performance of any study-related procedures including screening procedures. An up to 8-week period is provided for completing screening assessments and determining subject eligibility for the study. Subjects on stable diet known to the investigator and followed at the site may skip the 6-week diet run-in. Safety labs may be re-tested for determination of subject eligibility after consultation with the Sponsor Medical Monitor.

During the screening period, subjects will undergo a medical history and physical examination including vital signs, 12-lead ECG, and have blood and urine samples taken for clinical laboratory testing. Subjects will be screened for HIV, hepatitis B, and hepatitis C.

Eligible subjects will be on a stable low-fat diet (according to local clinical guidelines) beginning at least 6 weeks prior to the first dose of Study Drug. The diet stabilization period may be reduced if the patient is following a stable low fat diet for optimal disease control and disease management prior to screening.

Subjects meeting eligibility criteria at Screening will receive standardized meals in preparation for the pre-dose postprandial analysis to be performed on Day -1.

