### **6.1.2 Treatment Period**

Subjects will be managed on an outpatient basis. Safety and clinical laboratory evaluations as well as blood sampling for PK analysis will be performed periodically throughout the treatment period. Any AEs and concomitant medications will be recorded.

*Postprandial Assessment (Appendix E):* Postprandial assessments will be performed at Day -1 and at Week 14. Subjects will consume standardized pre-cooked meals (lunches and dinners (provided) and instructions for breakfasts and snacks) for the 2 days prior to the post-prandial evaluations. Patients will remain fasted after consuming the standardized pre-cooked meal for the dinner on the evening prior to their visit. Alcohol consumption is not allowed for the 2 days prior to the post-prandial evaluations. On each of the post-prandial evaluation days, following the first blood draw, patients will consume a standardized liquid meal (which represents about a third of the daily caloric requirements) containing a radioisotope tracer, followed by an 9 hour infusion of two stable isotope tracers and serial blood sampling. Patients will receive a standardized pre-cooked meal 9 hrs after consuming the liquid meal, after which they will fast until the 24 hour blood draw the following day.

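### The first tritium-labelled meal precedes the Day 1 pregnancy re-test, and no limit tighter than the 56-day eligibility window applies to the Screening result it relies on

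*Combined protocol and SAP*

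**What the plan says.** All references are to the Amendment 1 protocol.

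- **Tracer meals.** Section 6.1.2 states: "Postprandial assessments will be performed at Day -1 and at Week 14". Appendix E describes a liquid meal carrying 300 µCi of 3H-palmitate. Its sampling table puts the first meal on Day -1 and only the 24-hour draw on Day 1. Footnote a to that table allows the first meal to be earlier, though as near to Day 1 as possible.
- **Lead-in.** Section 6.1.1: "Subjects meeting eligibility criteria at Screening will receive standardized meals in preparation for the pre-dose postprandial analysis to be performed on Day -1". Appendix A footnote l adds that the subject "will return to the study center on Day -1 (2 days after consumption) for pre-dose postprandial assessments". The consumption meant there is of the preparatory standardized meal; the labelled meal is given at the visit itself.
- **Gate.** Footnote l also says: "The postprandial assessment for Screening will only be performed after other eligibility criteria are met". Section 5 accepts criteria met within 56 days of Day 1.
- **Pregnancy tests.** The "Serum Pregnancy Test" row of Appendix A has entries at Screening, Day 1 and Days 29, 57, 85, 92, 120, 148 and 176. Footnote k restricts it: "Women who are not surgically sterile or post-menopausal".
- **Order within a visit.** Appendix A: "All procedures and study samples are to be performed pre-dose at respective visits, unless specified". The timing note below the footnotes makes Study Drug administration the reference point.
- **Second meal.** After the Week 14 visit, subjects "will return to the site 2 days later (Day 94) plus one more day (Day 95) for post-dose postprandial assessments".

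**The concern.** Pregnancy is an exclusion, and the plan re-tests on Day 1 before the first dose. The radioactive meal, which is a research procedure with no therapeutic purpose, comes at least a day before that re-test. A site that follows the plan exactly may give the tracer on the strength of a test done weeks earlier. If contraception fails during screening and nobody suspects a pregnancy, the exposure comes first and the Day 1 sample is the first scheduled chance to detect it.

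If that sample were positive, the patient could not properly go on to treatment, and her tracer data would have no post-treatment counterpart. The matter is a participant safeguard; it has no bearing on the analysis of patients who do proceed.

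**Working it through.** **Inputs**

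- Screening window: 56 days, or 8 weeks (Section 3.4.1; Section 5).
- First tracer meal: Day -1, or Day -k if earlier (Section 6.1.2; Appendix E footnote a).
- Standardized meals for the 2 days before the assessment, issued once eligibility is met (Sections 6.1.1 and 6.1.2).
- Diet run-in: at least 6 weeks before the first dose, but it may be reduced or skipped for subjects already on a stable diet (Section 6.1.1).
- Week 14 visit: nominal Day 92, window ±2 days. Second meal: Day 94, window 0 (Appendix A; Appendix E).
- About 3 patients (Section 3.3).

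**The plan's own figure.** 8 × 7 = 56 days. With no Day 0, Day -56 to Day 1 is also 56 days, so the stated window reproduces.

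**Age of the Screening result at the first meal** = meal day minus sample day, both before Day 1:

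1. Longest, for a meal on Day -1: -1 - (-56) = 55 days.
2. Sample at the start of a 6-week run-in (Day -42): -1 - (-42) = 41 days. A run-in starting earlier in the window gives 41 to 55 days.
3. Shortest realistic: eligibility comes first, then 2 days of standardized meals, so the latest sample is about Day -3: -1 - (-3) = 2 days. A patient who skips the run-in can be near this end.
4. Meal moved to Day -k: the maximum is 56 - k days, for example 49 days at Day -7. The wait until the Day 1 test grows from 1 day to k days, so 7 days at Day -7.

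**Comparison within the plan**

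- On treatment, tests up to Day 85 are 28 days apart (Days 1, 29, 57, 85). The 55-day extreme is 55 / 28 = 1.96 times that interval.
- Second meal: footnote l gives 2 days (Day 92 to Day 94). Under the table's windows the sample could be on Days 90 to 94, a gap of 0 to 4 days.

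**Does any other text force a fresh result before the first meal?**

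- Footnote l's gate requires eligibility to have been met, but Section 5 lets that rest on a result up to 56 days before Day 1.
- The pre-dose rule puts the Day 1 sample ahead of Study Drug. It does not move it ahead of a meal given on an earlier day.
- The pregnancy test in Section 9.5.4 is triggered by suspicion only.
- Criterion 6 and Section 6.3.1 require abstinence or contraception from consent. They lower the chance of pregnancy but do not verify status.

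**The case against.** The strongest reply is that several safeguards already operate. A woman must be non-pregnant to pass the gate before the meal. If sexually active and of child-bearing potential, she must agree under criterion 6 to two highly effective contraceptive methods from consent. A suspected pregnancy prompts a test. A site may also test late in Screening, and patients already on a stable diet, which is plausible in this disease, may have a short gap. All of this stands and is why the point is minor. What remains is an unsuspected contraceptive failure between the Screening sample and the meal. The contraception safeguard is also less firm than criterion 6 suggests, since Section 6.3.1, to which it refers, accepts one or more methods.

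A reader might infer more than the documents support:

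- *That nothing limits the age of the Screening result.* The 56-day window does, and it is the source of the 55-day maximum.
- *That long gaps are typical.* The run-in waiver in Section 6.1.1 can shorten them greatly, and the protocol does not say how many patients would use it.
- *That a pregnancy would be known on Day 1 and the dose withheld.* The scheduled test is a serum test. No text says that the result is back the same day or that dosing waits for it.
- *That harm to a fetus is likely or large.* The protocol calls the tracer weakly radioactive and gives neither a fetal dose nor a conception risk.
- *That the second meal always follows a test by exactly 2 days.* The ±2-day window on Day 92 means the schedule is not uniform on this.

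**Conclusion.** The ordering gap is real under Amendment 1. The first tracer meal can rest on a pregnancy result about 2 to 55 days old, and the next scheduled test is on Day 1, after the exposure. The lower end assumes that eligibility is settled before the 2 days of standardized meals; the upper end assumes a sample on the first day of the window and a meal on Day -1.

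The number affected is 0 to about 3 women, depending on how many of the planned patients are neither surgically sterile nor post-menopausal. No probability of exposure can be stated from the documents. The co-infused glycerol and leucine tracers are stable isotopes and are not part of the point. Consent pages are not in the file, so any radiation precautions described there are not assessed.

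No endpoint, population or analysis rule is affected. This is a cheap improvement of minor severity: the case rests on the low cost of a fresh test, not on a claimed size of harm.

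**What to change.** In the Appendix A pregnancy-test row and footnote l, require the following for women who are neither surgically sterile nor post-menopausal: a negative pregnancy test from a sample taken within about 2 days before the pre-dose tracer meal, with the result available before the meal is given. A same-day local test on arrival is acceptable. Keep the Day 1 test before Study Drug.

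The 2-day limit is a choice, modelled on the nominal spacing at Week 14; the documents do not set it. As an option, also require the Week 14 result (nominal Day 92, ±2 days) to be available before the Day 94 meal, which adds no sample.

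The cost is one schedule entry and one or two sentences in footnote l. There is at most 1 extra test per affected woman, and none if the Screening sample already falls within the limit, so 0 to about 3 tests in total. The downside is that results must come back quickly, which may call for a local test.
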